4.4 Multiple Comparisons and Multiplicity

A Bonferroni correction will be explored for Immunogenicity model analysis (Section 15). Both adjusted and unadjusted p-values will be presented.

4.5 Handling of Missing Data

In general, all data will be analysed as collected and missing values will not be imputed or replaced unless stated otherwise.

4.6 Treatment Group and Visit Display Conventions

Summary Tables:

In summary tables, the representation as below:

Part A:

- Sentinels (*50mg once only*)

Part B:

- Group 1 (*50mg every 3rd day*)
- Group 2 (*50mg every 2nd day*)
- Group 3 (*50mg daily*)
- Overall (*Part B subjects*)

Data Listings:

In data listings, the following labels will be used:

Part A:

- Sentinels

Part B:

- Group 1
- Group 2
- Group 3

Visit labels:

The following visit labels will be used:

- Screening (Listing only)
- Day 1 (Listing only)
- Baseline (Table only)
- Day 2
- Day 3, Day 4, Day 5, Day 6, Day 7
- Day 8
- Day 9, Day 10, Day 11, Day 12, Day 13
- Day 14
- Day 28
- Early Termination (Listing only)
- Unscheduled (Listing only)

For listings, the visit representing baseline (either screening or unscheduled visit) will be marked as “[1]” with a footnote indicating it is baseline value. These visit displays will be sorted by date of visit within each participant.

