### 6.2 Part A (Sentinel Cohort)

On Day 1, 5 participants will be administered a single dose of LMN-301 intranasally to each nostril at a fixed dose of 50 mg (25 mg in each nostril) using the Unidose (UDS) Powder Nasal Spray System device (Aptar). Eligible participants will be admitted to the clinic on Day 1 prior to dosing, and will be observed as in-patients for 24 hours following study drug administration. Participants will be discharged on Day 2 and then followed on an outpatient basis for 14 days. Protocol-specified evaluations and procedures will be performed on Days 1-2 and then weekly or bi-weekly. Participants will be required to return to the clinic for an outpatient visit on Day 8. Telephone follow-up will be conducted on Days 3 to 7, with an end of study telephone follow up on Day 14.

There is no safety review committee for this study, however safety and tolerability data collected from the sentinel cohort participants will be reviewed by the principal investigator, the independent medical monitor, and the sponsor medical monitor, to decide whether to move forward with the multiple-dose cohorts (Part B). The discussion will include review of the study and individual stopping rules.

The schedule of assessments (SoA) for the sentinel cohort (Part A) is presented in [Table 21-A](#), with a description of study schedule and procedures provided in [Sections 10](#) and [11](#).

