### 6.3 Part B (Multiple Dose)

Up to 30 participants will be sequentially assigned to one of three dosing groups (10 participants per group) starting with Group 1. Participants will be administered LMN-301 intranasally to each nostril at a fixed dose of 50 mg (25 mg in each nostril) every third day for 12 days (Group 1), every other day for 12 days (Group 2) or every day for 12 days (Group 3). All study participants will be observed in the clinic for 4 hours after the first dose.

Participants will be monitored for the occurrence of any adverse events (AEs) and serious adverse events (SAEs). Vital signs, physical exams and safety/laboratory testing will be performed on Days 1, 3 or 4, 7 and 14. Participants will use a diary (paper or electronic) to record any symptoms from the first dose through 28 days after the first dose.

Serum will be collected on Days 1 (baseline before dosing and 2 hours after dosing), 3 or 4, 7 and 14 for analysis to detect systemic absorption of virus-binding proteins and anti-drug antibodies (ADA).

Nasal mucosal lining fluid (MLF) samples will be collected using Synthetic Absorptive Matrix (SAM) strips (Nasosorption™ FX-I, Hunt Developments (UK) Ltd, United Kingdom) from all participants on Day 1 (baseline before dosing and 2 hours after dosing), and on Days

3 or 4, 7 and 14. Nasal MLF samples will be sent to Lumen Bioscience (Seattle, WA, USA) for analysis.

The schedule of assessments (SoA) for part B is presented in [Table 21-B](#) with a description of the study schedule and procedures provided in [Sections 10 and 11](#).

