**Table 8-A LMN-301 Dosing of Study Participants in Study Parts A and B**

Cohort No.	Number of Participants to be Dosed with LMN-301	Dose delivered per actuation	Number of actuations per nostril (to be administered in each nostril)	Total Fixed Dose	Dosing Frequency	Total number of doses
Part A (Single dose)						
Sentinel cohort	5	25 mg	1	50 mg	Once only	1
Part B (Multiple dose)						
Group 1	10	25 mg	1	50 mg	Every 3 rd day, for 12 days	4

Cohort No.	Number of Participants to be Dosed with LMN-301	Dose delivered per actuation	Number of actuations per nostril (to be administered in each nostril)	Total Fixed Dose	Dosing Frequency	Total number of doses
Group 2	10	25 mg	1	50 mg	Every 2 nd day, for 12 days	6
Group 3	10	25 mg	1	50 mg	Daily, for 12 days	12

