## 13 STATISTICS AND DATA ANALYSIS

Detailed methodology for the summation and statistical analysis of the data collected will be documented in a separate Statistical Analysis Plan (SAP) that will be finalised before database lock. Any changes to the methods described in the final SAP will be described and justified as needed in the clinical study report (CSR).

This section describes the general framework to be used for the analysis and presentation of data in this study. The information described in this section may be revised during the study to accommodate protocol amendments and to make changes to adapt to unexpected issues in study execution and data that could affect planned analyses.

Generally, summaries will be presented separately for Parts A and B, with summaries presented by treatment group and overall for Part B.

For descriptive statistics, continuous data will be summarised by treatment arm and time point using the number of observations, arithmetic mean, standard deviation (SD), median, minimum and maximum. Discrete data will be summarised using counts and percentages.

All available data will be included in data listings. Data tabulations will be performed for specific analysis populations.

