3 SAMPLE SIZE

The total study sample size was selected to have a high probability of detecting one or more serious adverse events (SAE) if the SAE event rate is 10% or more. If the probability of an SAE is 10%, the probability of observing at least one event in N=35 subjects is over 97%. Looking at Part B only, if the probability of an SAE is 10%, the probability of observing at least one event in N=30 subjects is over 95%.

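### No planned table isolates events after the first dose in Part B, so single-dose event rates are tabulated only for the 5 sentinels although all 35 planned participants get the same first dose

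*SAP*

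**What the plan says.** The primary objective (Protocol 5, SAP 2.2.1) is the safety and tolerability of both single and multiple doses. For Part A, Protocol 6.2 states: "On Day 1, 5 participants will be administered a single dose of LMN-301 intranasally to each nostril at a fixed dose of 50 mg". For Part B, Protocol 6.3 gives the same amount per administration: "at a fixed dose of 50 mg (25 mg in each nostril) every third day for 12 days (Group 1", with the other two groups differing only in frequency. Protocol 10.3.1 has all three groups dosed on Day 1 with the same device. Under Protocol 8.5 the second dose falls on Day 2 in Group 3, Day 3 in Group 2 and Day 4 in Group 1.

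On reporting, Protocol 13 says: "Generally, summaries will be presented separately for Parts A and B, with summaries presented by treatment group and overall for Part B". SAP 4.6 follows this with columns for the sentinels, for each Part B group, and "Overall (*Part B subjects". The adverse event tables in SAP 13.1 use those columns and count all treatment-emergent events from the first administration onward. No table is restricted to the time before the second dose.

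The sample-size section (Protocol 13.1, SAP 3) aims at a "high probability of detecting one or more serious adverse events (SAE) if the SAE event rate is 10% or more". It says that "the probability of observing at least one event in N=35 subjects is over 97" percent and, for Part B, that "the probability of observing at least one event in N=30 subjects is over 95" percent.

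**The concern.** Until the second dose, a Part B participant is a single-dose participant: same dose, device and eligibility criteria. The planned tables do not use that fact. The only column in which every event follows exactly one dose is the sentinel column. In the Part B columns, events after the first administration are merged with events after the third, sixth or twelfth.

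Protocol 4.3 expects local reactions such as sneezing, nasal discharge, tenderness and irritation after administration. These are the events a first-dose window would capture. As planned, the report would give their single-dose frequency from 5 people, while 30 further first-dose observations appear only in listings.

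A smaller, separate matter is that the sample-size text leads with 35 participants, and no planned summary column has that denominator.

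**Working it through.** **Inputs.** Planned numbers: 5 in Part A and 10 in each of three Part B groups (Protocol Table 8-A). Doses per participant: 1, 4, 6 and 12 (same table). Serious adverse event rate for sizing: 10% (SAP 3). The documents give no expected rate for local reactions, so the 40% and 20% below are assumptions for illustration.

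**1. The plan's own figures.** P(at least one event) = 1 − (1 − p)^N with p = 0.10.
- N = 35: 1 − 0.9^35 = 97.5%, stated as over 97%. Reproduced.
- N = 30: 1 − 0.9^30 = 95.8%, stated as over 95%. Reproduced.

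The N = 30 figure has a matching column, Part B overall. The N = 35 figure has none.

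**2. What the Part B overall column mixes.** Planned administrations are 10×4 + 10×6 + 10×12 = 220, of which 30 are first doses (30/220 = 13.6%). The first-dose rate cannot be recovered from that column once events occur.

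**3. Precision when events occur.** Exact (Clopper-Pearson) 95% limits for x events in n: lower = Beta quantile 0.025 with parameters (x, n − x + 1); upper = Beta quantile 0.975 with parameters (x + 1, n − x).

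| Assumed rate | Data | x/n | Exact 95% CI |
|---|---|---|---|
| 40% | Sentinels only | 2/5 | 5% to 85% |
| 40% | Part B, first dose only | 12/30 | 23% to 59% |
| 40% | All, first dose only | 14/35 | 24% to 58% |
| 20% | Sentinels only | 1/5 | 1% to 72% |
| 20% | All, first dose only | 7/35 | 8% to 37% |

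Most of the gain comes from cutting Part B at the second dose. Adding the 5 sentinels contributes little more.

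**4. Precision when no events occur.** One-sided 95% upper bound = 1 − 0.05^(1/n): 45.1% for n = 5, 9.5% for n = 30, 8.2% for n = 35. If the sentinel and Part B overall columns both show zero, there were no events after the first dose in any of the 35. The fair comparison is then 9.5% against 8.2%, and a new table adds almost nothing.

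**5. Can the window be derived?** SAP 12 lists date and time of each administration, and SAP 13.1 lists start date and time of each adverse event. A window from first dose to the earlier of second dose and 24 h needs no new data. The 24 h limit is about the interval to Group 3's Day 2 dose.

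**6. Which Day 1 assessments can be pooled?**
- Vital signs: 30 min and 1 h appear in all schedules for both parts. The 4 h point is in both parts' Day 1 procedures and in footnote 11 of Table 21-B, but Table 21-F for Part B omits it. SAP 4.6 also limits the Day 1 visit label to listings, so read literally no table label covers Day 1 post-dose values in any column.
- SNOT-22: asks about the preceding two weeks (Protocol 11.15), so a score 2 h after dosing mostly describes the time before it.
- Nasal examination: planned as a listing only (Protocol 13.7.3, SAP 13.6). Protocol 11.12 has events recorded as adverse events in any case.

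**The case against.** The strongest reply is that this is a display choice in a descriptive study. The protocol sets separate reporting, the SAP follows it, every participant's data are listed with event times, and SAP 1 lets additional analyses be described in the study report. Part A is a sentinel gate with 24 h in-patient observation, while Part B has 4 h in clinic followed by a diary, so ascertainment differs for most of a 24 h window. No decision rule depends on a pooled column.

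Much of this stands. A reader might infer that the trial cannot use its own data for the single-dose half of its objective. The documents do not support that: the listings allow a count by hand, and no sentence confines single-dose conclusions to Part A. A reader might also contrast 45.1% with 8.2%, or 41.0% detection with n = 5 (1 − 0.9^5) against 97.5%, as the size of the problem. That overstates it, because the zero-event result is already visible from two printed columns. Nor does the 97% carry over to a first-dose table: it concerns serious events in 35 participants with no 24 h limit, and a 10% rate over participation is not a 10% rate within a day.

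What the reply does not answer is the case in which events do occur. Then the printed Part B counts cannot be separated by dose, and a pre-specified table is better than one assembled from listings after the results are known. The difference in observation is a reason for a footnote and for keeping the separate columns.

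**Conclusion.** The point holds as a worthwhile, low-cost improvement; no planned analysis is invalid. Acute single-dose event rates are tabulated for 5 people when 35 planned participants supply the same information. At an assumed 40% rate the interval narrows from 5%–85% to 24%–58%; at 20%, from 1%–72% to 8%–37%.

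This rests on the planned 35 being dosed, on local reactions being common enough for rates to matter, and on first-day ascertainment being similar enough in the two parts to pool with a footnote. The pooled table speaks to acute first-dose effects only. Beyond its window, the sentinels, followed to Day 14, remain the only source for later single-dose effects. The absence of a 35-participant column is a separate mismatch with the sample-size text, which a first-dose table would not repair.

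**What to change.** Add to SAP 4.6 and 13.1 a pooled table, *First dose, all participants (planned N=35)*, of solicited, unsolicited and serious treatment-emergent events with onset from the first dose to the second dose or 24 h, whichever is earlier, with exact 95% confidence intervals. State how an onset with a date but no time is assigned. Keep the part and group columns, and footnote the observation: 24 h in-patient in Part A, 4 h in clinic plus diary in Part B.

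Pool Day 1 post-dose vital signs only at time points confirmed as common to both parts. First reconcile the Part B 4 h time point (Protocol 10.3.1 and Table 21-B footnote 11 against Table 21-F) and the listing-only Day 1 label in SAP 4.6. Leave SNOT-22 and nasal examination out of the pooled table.

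Separately, if the N=35 sizing statement is to have a matching display, add an all-participants column to the overall summary of serious and other treatment-emergent events, labelled as mixing 1, 4, 6 and 12 doses and follow-up to Day 14 (Part A) and Day 28 (Part B).

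The cost is SAP wording and one or two extra displays from data already collected. Dosing, visits and sampling do not change.

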### *13.7.2 Vital Signs*

Observed values and changes from baseline for vital signs (systolic and diastolic blood pressure, pulse rate, oral temperature, and respiratory rate) will be summarised at each scheduled timepoint using descriptive statistics.

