### *13.7.7 Nasal Symptoms Sino-Nasal Outcome Test*

Scores will be totalled for all 22 symptoms. Changes from baseline in individual total SNOT-22 scores will be calculated as the post-baseline value minus the baseline value. Thus, a negative change will reflect an improvement in the corresponding score. Observed values and changes from baseline will be summarised at each scheduled timepoint by treatment using descriptive statistics and tabulated for each cohort (dose level) and overall.

Individual symptoms will be listed, with the 5 most important issues flagged. The total SNOT score will also be included in the listing.

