4.2 General Considerations

All data collected during the study (data originating from the electronic Case Report Forms (eCRFs) or electronic transfers will be presented in the data listings. Event-based listings will be sorted by treatment group, participant identifier and event start date/time (i.e., AE start date/time). Assessment-based listings will be sorted by treatment group, parameter name (alphabetically unless specifically stated otherwise), participant identifier, visit and time point (if applicable).

Unless otherwise stated, the following methods will be applied:

- Continuous variables: Descriptive statistics will include the number of non-missing values (n), arithmetic mean, standard deviation, median, minimum and maximum values. The minimum and maximum values will be displayed to the same decimal precision as the source data, the arithmetic mean and median values will be displayed to one more decimal than the source data, and the SD values will be displayed to two more decimals than the source data for the specific variable. The appropriate precision for derived variables will be determined based on the precision of the data on which the derivations are based, and statistics will be presented in accordance with the abovementioned rules.
- Categorical variables: Descriptive statistics will include frequencies and percentages per category. The denominator in all percentage calculations will be the number of participants in the relevant analysis population with non-missing data, unless specifically stated otherwise. Percentages will be rounded to one decimal place and will not be displayed for zero frequencies.
- Presentation of p-values and confidence intervals: 95% confidence intervals will be computed, and reported to four significant figures, p-values will be displayed up to three decimal places and as “<0.001” if the value is below 0.001.
- Repeat/unscheduled assessments: Only values collected at scheduled study visits/time points will be presented in summary tables. If a repeat assessment was performed, the result from the original assessment will be presented as the result at the specific visit/time point. All collected data will be included in the data listings. If an unscheduled visit was intended to replace the missing assessment for a scheduled visit this should be documented clearly before values are carried forward as a scheduled visit assessment.

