4.3 Key Definitions

The following definitions will be used:

- Date of the First Study Treatment Administration: The date of the first study treatment administration is defined as the earliest date on which a study treatment was administered.
- Date of the Last Study Treatment Administration: The date of the last study treatment administration is defined as the latest known date on which a study treatment was administered.
- Baseline: The Baseline value is defined as the last available valid, non-missing observation (including repeat and unscheduled assessments) for each Participant prior to first study treatment administration on Day 1.

For ECG triplicates, the baseline is defined as the mean of the last set of triplicates performed prior to first study treatment administration.

For SNOT-22 results, the baseline is defined as the total score (as defined in section XX) of the last SNOT-22 test performed prior to first study treatment administration.

- Change from Baseline: The change from Baseline value is defined as the difference between the result collected/derived at a particular visit and the Baseline value.

The change from Baseline value at each visit will be calculated for all continuous parameters using the following formula:

$$\text{Change from Baseline Value} = \text{Result at specified visit} - \text{Baseline Value}$$

The change from Baseline value will only be calculated if the specific visit result and the Baseline value for the parameter are both available and will be treated as missing otherwise.

- Study Day: The study day of an event is defined as the relative day of the event starting with the date of the first study treatment administration (reference date) as Day 1 (there will be no Day 0).

The study day of events occurring before the first study treatment administration will be calculated as:

Study Day = (Date of Event - Date of First Study Treatment Administration)

For events occurring on or after Day 1, study day will be calculated as:

Study Day = (Date of Event - Date of First Study Treatment Administration) + 1

Study days will only be calculated for events with complete dates and will be undefined for events that are 'Ongoing' at the end of the study.

- Actual Time from First Dose (hours) in PK related outputs is defined as:

$$(\text{Date/Time of PK Sample collection}) - (\text{Date/Start Time of First Dose on Day 1})$$
- Actual Time Deviation (hours) in PK related outputs is defined as:

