13.3 Vital Sign Assessments

The following vital signs measurements will be taken at the time points specified in the study procedure schedule:

- Systolic blood pressure (SBP) (mmHg) [Reference range: 90-160 mmHg]
- Diastolic blood pressure (DBP) (mmHg) [Reference range: 50-95 mmHg]
- Pulse Rate (beats/min) [Reference range: 45-100 beats/min]
- Temperature (°C) [Reference range: 35.5-27.7 °C]
- Respiratory Rate (breaths/min) [Reference range: 12-22 breaths/min]
- Overall Clinical Interpretation:
 - Normal
 - Abnormal NCS (Not Clinically Significant)
 - Abnormal CS (Clinically Significant)

The parameter names that will be used in the outputs will comprise of the test name and the unit of measure, for example, 'Systolic Blood Pressure (mmHg)'. Parameters will be sorted in the order that the measurements were collected in on the Vital Signs eCRF page within the tables and listings.

Summary statistics for vital sign parameters in accordance to section 4.2 will be presented for baseline and for each scheduled post baseline visit (which also includes change from baseline). In addition, overall clinical interpretation result (Normal, Abnormal Not Clinically Significant (NCS), Abnormal Clinically Significant (CS)) will be summarized by counts and percentages for baseline and each scheduled post baseline visit. These summary tables will be generated using the SS population for treatment groups defined in Section 4.6.

In addition, shift tables from baseline at each visit for vital sign parameters (normal, low and high) will also be presented using counts and percentages.

The listing of vital sign parameters will include all the information collected. In addition, the observations that are used as the baseline record for each parameter will be flagged, and the change from baseline values at each post baseline (scheduled and unscheduled) visit will be presented. This listing will be presented by treatment groups defined in section 4.6, sorted by participant ID and visit for the SS population, along with age, sex, race, and baseline weight of the participant.

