| (-28 to 0) | Day 1 | Day 2 | Day 3-7 | Day 8 | Days 9-13 | Day 14 | |
| Visit Window (days) | | | | ±1 | | ±1 | |
| Unsolicited AEs/SAEs ⁶ | X | X | X | X | X | X | |
| Review diary ¹⁵ | | X | | X | | X | |
| Sino-Nasal Outcome Test (SNOT-22) ⁸ | X | X | | X | | | |
| Telephone follow-up ⁹ | | | | X ⁹ | | | |

Abbreviations: AE=adverse event; BMI=Body mass index; ECG=Electrocardiogram; EoS=End of study; FSH=Follicle stimulating hormone; HBsAg=Hepatitis B surface antigen; HCV=Hepatitis C virus; HIV=Human immunodeficiency virus; RAT=Rapid Antigen Test; SAE=serious adverse event; WOCBP = women of childbearing potential.

1. Vital signs to be measured at pre-dose, and 30 min, 1 hr and 4 hr post-dose on Day 1.
2. Urine toxicology screen for drugs of abuse. Urine tox screen and alcohol breath test to be performed at any time pre-dose on Day 1.
3. Serum for detection of study drug will be collected before and 2 hours (± 15 mins) after dosing on Day 1, and prior to discharge on Day 2, and during clinic visit on Day 8.
4. Serum for anti-drug antibodies will be collected pre-dose and 2 hours (± 15 mins) on Day 1, prior to discharge on Day 2, and during clinic visit on Day 8.
5. Intranasal mucosal lining fluid (MLF) samples will be collected before and 2 hours (± 15 mins) after dosing on Day 1, and once prior to discharge on Day 2, and during clinic visit on Day 8.
6. Participants will be provided with a diary to record any solicited and/or unsolicited AEs, and to record concomitant medication usage. Participants will be instructed by site staff on completion during in-person visits
7. Solicited local AEs: stuffy nose, runny nose, sneezing, nasal irritation, nasal tenderness/pain, loss of smell, sore throat scratchy throat, cough
8. Sino-Nasal Outcome Test should be completed at Screening, at 2 hours (± 15 mins) post-dose on Day 1, and during clinic visit on Day 8.
9. Research staff to perform daily telephone calls to participants from Days 3-7.
10. Urinalysis and 12-lead ECG to be performed at Screening and at End of Study. Hematology, serum chemistry and coagulation on Day 1 to be performed any time pre-dose.
11. Targeted physical examination to be performed within 1 hour pre-dose. Nasal examination to assess swelling of the mucosa, erythema, and secretions to be performed using nasal speculum and headlight within 1 hour pre-dose and 3 hours post-dose on Day 1.

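### Read literally, SAP 4.6 leaves the Day 1 post-dose vital signs and 2-hour SNOT-22 out of the safety tables, and SAP 13.3 misprints the temperature range

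*SAP*

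**What the plan says.** SAP 4.6 sets the visit labels for all outputs. Day 1 appears as "Day 1 (Listing only", Baseline is for tables only, and the next label is Day 2. No post-dose time-point label is given. The baseline footnote rule in the same section refers to "the visit representing baseline (either screening or unscheduled visit" and does not name the Day 1 pre-dose record.

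SAP 4.3 defines Baseline as the last valid value "prior to first study treatment administration on Day 1".

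SAP 13.3 says vital-sign summaries "will be presented for baseline and for each scheduled post baseline visit". It adds low/normal/high shift tables by visit and prints the temperature reference range as 35.5-27.7 °C. Protocol 11.13 gives 35.5 to 37.7 °C.

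Other passages point towards tabulating by time point:

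- SAP 4.2: "Only values collected at scheduled study visits/time points will be presented in summary tables".
- Protocol 13.7.2, on vital signs: "will be summarised at each scheduled timepoint using descriptive statistics".
- Protocol 13.7.7, on SNOT-22: "Observed values and changes from baseline will be summarised at each scheduled timepoint by treatment using descriptive statistics".
- SAP Appendix 18.1, footnote 1 (Part A): "Vital signs to be measured at pre-dose, and 30 min, 1 hr and 4 hr post-dose on Day 1". Footnote 8 there adds a SNOT-22 two hours after dosing on Day 1.
- SAP Appendix 18.2, footnotes 11 and 17 (Part B): Day 1 vital signs at 15 min, 30 min, 1 h and 4 h post-dose, and SNOT-22 two hours after dosing.

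SAP 16 declares one change from the protocol, on the analysis set for compliance and exposure.

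**The concern.** A post-dose Day 1 value cannot be Baseline, because Baseline is pre-dose. It cannot appear under Day 1 either, because that label is reserved for listings. A programmer following SAP 4.6 to the letter would therefore have no row for it in any summary or shift table. That conflicts with the protocol and sits badly with SAP 4.2, and it is not declared.

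SAP 2.2.1 makes changes from baseline in vital signs and SNOT-22 primary endpoints. Day 1 also holds the only vital signs that the protocol fixes within 4 hours after a dose. Under Protocol 10.3.2 and Table 21-B footnote 16, the later Part B dosing-day readings are taken before dosing. Table 21-F instead allows any time on the day, and those passages must be reconciled. The tables could thus omit the period in which an acute group-level change would be most likely to show.

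The temperature range is a separate, smaller slip in the section that plans the vital-sign shift tables. An upper limit below the lower limit cannot be used to classify anything.

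**Working it through.** The plan gives no figure of its own on this point, so the check is a count of scheduled post-baseline assessments against the table labels in SAP 4.6 (Baseline, Days 2 to 14, Day 28).

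**Vital signs.** The protocol's schedules differ, so each is counted.

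| Part and source | Post-baseline time points | Without a table label |
|---|---|---|
| A: section 10.2, Table 21-A | 30 min, 1 h, 4 h, Day 2, Day 8, Day 14 | 3 of 6 |
| A: Table 21-E (stops at Day 8) | 30 min, 1 h, 4 h, Day 2, Day 8 | 3 of 5 |
| B: section 10.3 | 15 min, 30 min, 1 h, 4 h, Day 3/4, Day 7, Day 10/11, Day 14, Day 28 | 4 of 9 |
| B: Table 21-B footnote 11 (no Day 10/11) | 15 min, 30 min, 1 h, 4 h, Day 3/4, Day 7, Day 14, Day 28 | 4 of 8 |
| B: Table 21-F (also no 4 h) | 15 min, 30 min, 1 h, Day 3/4, Day 7, Day 14, Day 28 | 3 of 7 |

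Planned sets affected, with 5 participants in Part A and 30 in Part B:

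- lower: 5 × 3 + 30 × 3 = 15 + 90 = 105 (Table 21-F)
- upper: 5 × 3 + 30 × 4 = 15 + 120 = 135

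**SNOT-22.** Baseline is the screening questionnaire, since none is scheduled before dosing on Day 1.

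- Part A: Day 1 at 2 h and Day 8, so 1 of 2 has no label.
- Part B: Day 1 at 2 h, Day 7, Day 14 and Day 28, so 1 of 4 has no label. The Day 7 questionnaire, also 2 h post-dose, keeps its row.
- Planned questionnaires affected: 5 + 30 = 35.

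**First tabulated vital signs after a dose.**

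- Part A: Day 2 at 24 ± 2 h, so 22 to 26 h.
- Part B, assuming readings within 1 h before dosing and dosing at the same clock time each day:
  - Group 1, Day 4: 72 h less 0 to 1 h = 71 to 72 h after the previous dose
  - Group 2, Day 3: 48 h less 0 to 1 h = 47 to 48 h
  - Group 3, Day 3: 24 h after the Day 2 dose, less 0 to 1 h = 23 to 24 h

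**Temperature.** SAP 4.3 writes its rule only for laboratory parameters: Low below the lower limit, High above the upper limit, Normal otherwise. The same rule is assumed here for vital signs.

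- Normal under the printed range needs 35.5 ≤ x ≤ 27.7, which no x satisfies.
- 35.5, 36.8, 37.7 and 38.5 °C all exceed 27.7 and are all High. A rise from 36.8 to 38.5 °C would be shown as High to High.
- Under Protocol 11.13, 35.5, 36.8 and 37.7 °C are Normal and 38.5 °C is High, so the same rise is Normal to High.

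**The case against.** The best defence is that SAP 4.6 is a display convention and not a rule on what is analysed. The list looks generic: it has labels for days such as 5, 6 and 13, when no vital signs or SNOT-22 are scheduled. Listing-only Day 1 followed at once by table-only Baseline can be read as one relabelling, in which the Day 1 pre-dose record appears in tables as Baseline. SAP 4.2 mentions time points, and the silence of SAP 16 suggests that no departure was intended. Table shells, which might settle the rows, are not among the documents.

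Part of this stands. Nothing shows a deliberate decision to drop the data, and for vital signs the relabelling reading is possible. It does not work for SNOT-22, which has no scheduled pre-dose Day 1 assessment, so for that instrument a scheduled Day 1 record can only be the post-dose one. The baseline footnote does not support the relabelling either, because it omits the Day 1 pre-dose record. The SAP 4.2 sentence limits what tables may show; it supplies no row for Day 1.

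Four points limit the weight of the concern, and all are fair:

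- SNOT-22 asks about the preceding two weeks, so a score taken 2 h after dosing mostly describes the pre-dose period. The vital signs matter more.
- The shift tables are an addition in the SAP; Protocol 13.7.2 asks only for observed values and changes from baseline.
- The study is open-label and descriptive, with 5 or 10 participants per group. Every value is listed, and clinically significant findings are recorded as AEs.
- The temperature range is an obvious misprint that a programmer would probably query.

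**Conclusion.** The concern holds as an inconsistency within the SAP and an undeclared departure from Protocol 13.7.2 and 13.7.7, on the literal reading of SAP 4.6. On that reading, between 3 of 7 and 4 of 8 post-baseline vital-sign time points in Part B, and 3 of 6 or 3 of 5 in Part A, have no row in the tables for a primary safety endpoint. The SNOT-22 loss is 1 of 2 in Part A, leaving only Day 8, and 1 of 4 in Part B. The schedule discrepancies change the denominators but not the conclusion.

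The consequence is confined to the summary and shift tables. Listings, AE reporting and sample size are unaffected. The temperature error affects only the temperature shift table, and only if it is programmed as printed with the laboratory rule; means and changes from baseline are untouched. Whether the rows would really be missing depends on how the programmer reads SAP 4.6, and the plan should not leave that open.

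**What to change.** 1. In SAP 4.6, add table labels for each scheduled Day 1 post-dose time point: vital signs at 30 min, 1 h and 4 h in Part A; at 15 min, 30 min, 1 h and 4 h in Part B, once Table 21-F has been reconciled with Protocol 10.3.1 and Table 21-B footnote 11; and the 2-hour SNOT-22 in both parts.
2. In SAP 4.6, keep the listing-only restriction for the Day 1 pre-dose record that serves as Baseline, and name that record in the baseline footnote.
3. In SAP 13.3, refer to each scheduled post-baseline visit and time point, for both the summary and the shift tables.
4. If leaving these rows out is intended, declare it with the reason in SAP 16.
5. In SAP 13.3, correct the temperature range to agree with Protocol 11.13 (35.5-37.7 °C).

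The cost is a few lines of SAP text, three or four more rows in each vital-sign table and one more SNOT-22 row. No new data are needed, because the Day 1 values are already collected and listed.
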